Preliminary analyses prior to the longitudinal regression modeling will evaluate Treatment group differences at baseline in both the RCT and Observational cohorts in the RCT study, observed differences in HRQOL or personal demographics will evaluate the success of the randomization in the OBS study, observed differences in HRQOL and/or personal demographics will inform decisions regarding what covariates should be used to control for these baseline differences to allow better interpretation of longitudinal treatment differences. These analyses are likely to be done using recursive partitioning rather than stepwise regression methods, which, of late, have fallen into disfavor.

Sample size calculations to ensure adequate power were conservative by focusing on the ability to detect statistically significant differences between treatment groups at any specific follow-up interval. These are essentially a priori tests of simple effects of a treatment by time interaction, which is the primary focus of the study. These analyses are considered conservative for two primary reasons.

These differences are "between subjects" effects, meaning that the added power associated with repeated assessments across time do not help to increase power

The standard assumed standard deviations in the calculations did not consider the standard deviation estimate shrinkage likely to result from the included baseline covariates (mostly baseline outcome).

1.6.1 General Analysis Strategy: Our approach to data analysis includes three consecutive stages. Most analyses will be performed using SAS software, which has a wide range of statistical routines and offers great flexibility in data manipulation.

Stage 1 – Descriptive Analysis:

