The models describing the experiences of nonoperative and operative patients, discussed under Aim 1, will be expanded to determine if the time trends depend on baseline covariates, including age group, gender, socioeconomic status, education level, and comorbidities, including BMD, BMI, and mental health status. Each baseline predictor initially will be added to the model separately, to determine its association with the outcome trend. We will then use a backward selection procedure to reduce a “full” multivariate model that includes all baseline variables that are found to be statistically significant in the univariate analyses, to a “parsimonious” model that includes only baseline variables that remained statistically significant in the multivariate analysis. For these analyses, “statistical significance” will be assessed at the 0.10 levels, in order to err on the side of including baseline characteristics that may predict outcome. Note that our purpose here is not significance testing; rather, the p-value is used to screen for covariates that are prognostic. We will summarize these findings using predicted levels of change in HRQOL generated by the models. These models will be used to characterize patients who achieve exceptionally good outcomes and those who achieve exceptionally poor outcomes. These results will be useful to clinicians in identifying patient prognoses.

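### Aim 2's prediction model has no shrinkage, calibration check or internal validation, so its predictions for clinicians are expected to be too extreme

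*SAP*

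**What the plan says.** SAP section 1.6.1, Stage 3, Specific Aim 2 extends the Aim 1 longitudinal models to ask whether time trends depend on baseline covariates, "including age group, gender, socioeconomic status, education level, and comorbidities, including BMD, BMI, and mental health status". That names seven candidates and leaves the list open.

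The procedure has two steps. First, "Each baseline predictor initially will be added to the model separately". The full model then "includes all baseline variables that are found to be statistically significant in the univariate analyses". Second, "We will then use a backward selection procedure to reduce a" full model to a shorter one. Significance in both steps "will be assessed at the 0.10 levels, in order to err on the side of including baseline characteristics that may predict outcome". The SAP adds that the aim here is prognostic screening and not hypothesis testing.

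The output is model-predicted HRQOL change, used to describe patients who do unusually well or badly. The SAP says of it: "These results will be useful to clinicians in identifying patient prognoses". The Aim 2 statement goes further and wants a model that identifies who is likely to benefit from each approach.

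Elsewhere, SAP section 1.6 says that the preliminary comparisons of baseline differences are likely to use "recursive partitioning rather than stepwise regression methods, which, of late, have fallen into disfavor".

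**The concern.** A model fitted by ordinary maximum likelihood and reported on the data that built it fits those data better than it will fit new patients. Its predictions spread too far from the mean: the good prognoses look too good and the poor ones too poor. With modest samples and modest predictors the gap can be large. Shrinkage corrects it in part, and internal validation shows how large it is.

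The SAP has neither. It uses the word *shrinkage* once, in section 1.6, about the standard deviation in the power calculation. It uses *bootstrap* once, in the Addendum of 1/17/13, about sample size. In the Protocol, *validated* describes questionnaires. Section 1.6.3 compares the randomized and observational results to judge whether the trial results generalize, and does not present this as a test of the Aim 2 model.

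The tails of prediction are what Aim 2 intends to describe and hand to clinicians, and they are where over-extreme predictions do most harm. The plan has no step that would show a reader how far to trust them.

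**Working it through.** **Inputs from the documents.** Selection level 0.10 and seven named candidates (SAP 1.6.1, Aim 2). Observational cohort at analysis: 77 + 93 = 170 (SAP 1.6.3). Randomized cohort: 63 enrolled (Addendum 1/17/13) with 10% loss by 2 years (SAP 1.6.3), so 63 × 0.9 = 56.7, about 57. Pooled: 170 + 57 = 227. One observational arm: 170 / 2 = 85.

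**The plan's nearest figure.** Aim 2 has no sample size or performance target. The SAP does state the observational cohort's power: 80% for a difference of 0.175, SD 0.400, groups of 77 and 93, two-sided 0.05.
- SE = 0.400 × √(1/77 + 1/93) = 0.0616.
- 0.175 / 0.0616 = 2.84. Normal approximation: Φ(2.84 − 1.96) = 81.0%. Noncentral t: 80.6%.

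The stated 80% is reproduced. It concerns a treatment difference and says nothing about prediction.

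**Screening when nothing matters.** With k independent null candidates, the chance that at least one passes is 1 − 0.90^k: 52% for k = 7 and 77% for k = 14.

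**Calibration slope.** The planned selection (univariate p < 0.10, then backward elimination at 0.10, unpenalised fit) was simulated 1,500 times per setting, and the slope was evaluated in the true population. A slope below 1 means that predictions are too extreme. Assumptions not in the documents: one continuous 24-month change score; 7 or 14 candidates (14 could be the seven plus their treatment interactions); pairwise correlation 0.2; half the candidates prognostic; true R2 of 5% to 30%.

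Median slope at true R2 of 5% / 10% / 20% / 30%:

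| n | 7 candidates | 14 candidates |
|---|---|---|
| 57 | 0.40 / 0.54 / 0.70 / 0.79 | 0.31 / 0.45 / 0.58 / 0.68 |
| 85 | 0.48 / 0.63 / 0.77 / 0.86 | 0.39 / 0.53 / 0.67 / 0.75 |
| 170 | 0.63 / 0.77 / 0.89 / 0.94 | 0.52 / 0.65 / 0.80 / 0.86 |
| 227 | 0.69 / 0.81 / 0.92 / 0.96 | 0.58 / 0.70 / 0.83 / 0.89 |

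The median is below 1 in every setting, and 66% to 100% of runs fall below 1. At n = 170, seven candidates and R2 10%, predicted departures from the mean are about 1 / 0.77 = 1.3 times too large.

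**Apparent against true fit.** With 8 candidates, 3 of them real, and true R2 10%, apparent R2 against R2 in new patients was 14% against about −2% at n = 57, 11.5% against 5.5% at n = 170, and 11% against 7% at n = 227. With stronger predictors at n = 170 the gap is small: 21% against 17% (true R2 20%) and 31% against 28% (true R2 30%).

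**Is selection the cause?** Selected model against unpenalised full model, R2 10%:
- 7 candidates: 0.54 against 0.46 (n = 57); 0.77 against 0.74 (n = 170); 0.81 against 0.80 (n = 227).
- 14 candidates: 0.45 against 0.26; 0.65 against 0.57; 0.70 against 0.63.

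The full model is worse at every sample size and every non-zero R2 examined.

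**Does shrinkage help?** The selected model was shrunk by a bootstrap calibration slope, with the selection repeated in every resample (7 candidates, 150 runs, 60 resamples). Median slope before and after:

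| n | R2 10% | R2 20% |
|---|---|---|
| 57 | 0.56 to 0.68 | 0.69 to 0.81 |
| 170 | 0.78 to 0.91 | 0.89 to 0.96 |
| 227 | 0.83 to 0.94 | 0.92 to 0.97 |

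**The case against.** The best defence is that the SAP says its purpose here is prognostic screening and that 0.10 is deliberately inclusive. That answers a complaint about false-positive tests. It does not answer one about exaggerated predictions.

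A second defence is that the effect may be mild. This stands in part. With both cohorts pooled and strong predictors the median slope reaches 0.96, and about one run in three is not too extreme. Section 1.6.3 also places covariate work in the larger observational cohort, so the figures for the randomized cohort alone are the unfavourable end. But pooling is itself an assumption, since the Addendum of 8/29/12 first evaluates the cohorts separately, and the plan has no check to show which case applies.

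A third is that the simulation is not the planned model. The SAP keeps baseline score, treatment, interval, site, age and sex in a longitudinal fit; the simulation has one time point and none of these. The figures are therefore illustrative. Testing time trends adds parameters, which would usually worsen overfitting.

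A reader might infer four stronger points that the documents do not support:
- *That the SAP rejects stepwise methods and then uses one.* The remark in section 1.6 is tentative and concerns covariates for baseline differences. Because backward elimination is a stepwise method, it shows an inconsistency of preference, but breaches no rule for Aim 2.
- *That screening and elimination are the root cause.* The unpenalised full model is at least as over-extreme.
- *That the reported fit is mostly optimism.* At n = 170 and true R2 10%, about half of the apparent fit is lost (11.5% to 5.5%), and far less with stronger predictors. The description suits only the randomized cohort alone with weak predictors.
- *That age is cut at 60 and information is lost.* Aim 2 names age group without giving a cut. The split at 60 is a randomization stratum in Protocol section 1.3. The base model in the Addendum of 8/29/12 already keeps age as a preplanned covariate, and Stage 2 of section 1.6.1 allows a quadratic in age.

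**Conclusion.** The concern holds as an omission: Aim 2 presents predictions for clinical use without shrinkage, optimism correction, a calibration check or internal validation. Over-extreme predictions and an over-favourable fit are the expected result, though not a certain one. Under the stated assumptions the median calibration slope is about 0.3 to 0.8 for the randomized cohort alone, 0.5 to 0.95 for the observational cohort and 0.6 to 0.96 pooled. The direction was the same in every setting. The size is uncertain, because the documents fix neither the number of candidates, nor the predictive strength, nor the cohort used for Aim 2. The point does not touch the Aim 1 treatment comparison. It is a cheap improvement that should be made before any Aim 2 predictions are published.

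**What to change.** In SAP section 1.6.1, Specific Aim 2:

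1. Fit the listed baseline variables with penalisation (ridge or lasso), or keep the planned selection and apply a bootstrap-estimated shrinkage factor to the resulting model.
2. Bootstrap the entire model-building procedure, with any screening and elimination repeated in every resample.
3. Report optimism-corrected R2 and calibration slope before presenting predicted outcomes or describing the patients at either extreme.
4. State which cohort or cohorts the model uses and close the list of candidates, including any treatment interactions.
5. Label predictions from the randomized cohort alone as exploratory, because shrinkage restores calibration only partly at about 57 patients.

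Do not simply replace selection with an unpenalised full model.

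The cost is extra analysis code and no new data. The downside is a less favourable reported fit.

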Evaluating the statistical power for a mixed model longitudinal analysis is not straightforward. One conservative approach is to power the study with regard to a simple effects test associated with the highest order effect of interest in the study, here the Treatment x Assessment Time interaction. In this case, the sample size for the two treatment groups is estimated and, since the two treatment groups are not matched, the sample size per treatment group is likely to be larger than would be required to establish a significant change in outcome within a Treatment group across Assessment Time simple effects test (e.g., difference in SRS scores from baseline to 2-year follow-up). Accordingly, this study was powered with respect to the simple effects tests associated with a significant Treatment x Assessment Time interaction at the primary 2-year endpoint. This power analysis is informed by the data already gathered by the SDRG with the mean and standard error estimated adjusted for SRS baseline and patient age gender and Cobb angle. **Table 2 summarizes estimated sample sizes per treatment needed to achieve power of .80 for 2-tailed testing with type I error rate set at .05 under a variety of effect sizes, based on mean and standard deviation estimates.** The two rows highlighted were judged to reflect the most likely scenarios and, overall, the sample size of 30 per group in the RCT was considered a reasonable choice for achieving sufficient power to detect a real difference between the two treatment groups at 2-years follow-up.

Table 2

Estimated Means		Common SD	Effect Size	N per Group
Trt 1	Trt 2			
0.3	0.8	0.6	0.833	24
0.4	0.8	0.6	0.667	37
0.5	0.8	0.6	0.500	64
0.3	0.8	0.7	0.714	32
0.4	0.8	0.7	0.571	50
0.5	0.8	0.7	0.429	87

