For the observational cohort, applying the patterns suggested above (270 willing to participate) it follows that 188 would be willing to participate in the preference trial. If we assume a 1:1 surgical preference, which is not unreasonable given the SDSG preliminary data, this would result in 94 non-operative cases and 94 operative cases. Assuming a 10% crossover to surgery from non-operative care, this would result in 85 non-operative and 103 operative cases and, with 10% lost to follow-up, the final expected cell counts would be 77 and 93. In these circumstances, a two-group t-test with a 0.050 two-sided significance level will have 80% power to detect a difference in means of 0.175, assuming that the common standard deviation is 0.400, when the sample sizes in the two groups are 77 and 93, respectively (a total sample size of 170). An observational cohort of this size will supplement the RCT very well in that longitudinal analyses of these data will support evaluation of a number of covariates. Furthermore, similarities and differences in results between the RCT and observational study will provide some foundation for establishing (or not) the generalizability of the RCT results to the clinical case where randomization to treatment is not practiced.

Table 3: Breakdown of Enrollment from Five Centers, 2004 through 2006, According to Age Group and Intervention Arm

	Nonoperative (N=155)						Operative (N=141)					
	2004 (N=59)		2005 (N=43)		2006 (N=53)		2004 (N=41)		2005 (N=41)		2006 (N=59)	
	40-59	60-80	40-59	60-80	40-59	60-80	40-59	60-80	40-59	60-80	40-59	60-80
Washington University, St. Louis, MO	9	5	0	3	3	4	14	2	14	10	16	8
Emory Spine Center, Atlanta, GA	13	6	4	7	8	7	13	3	4	4	9	8
Leatherman Spine Institute, Louisville, KY	6	9	4	4	8	8	0	5	4	1	5	2
Univ. of Virginia, Charlottesville, VA	1	6	6	12	1	8	1	2	0	3	3	2
New York University, New York, NY	2	2	1	2	2	4	1	0	1	0	1	5
TOTAL	31	28	15	28	22	31	29	12	23	18	34	25

1.6.4 Stopping Rule protocol:

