Treatment = is a fixed effect with 2 levels the operative or non-operative care of the patient

Interval = is a fixed effect with X levels (depending on the outcome) indicating the follow-up times for collected patient outcomes

Time = The number of days between the date of assessment within an interval and the date of Intervention

site = the study site enrolling the patient (note site interactions may not be estimable in which case the interaction effects with site would be removed from the model)

age = a preplanned covariate

sex = a preplanned covariate

delta = a random effect reflecting the distance (in days) of the observed score in an interval from the center of the interval

Comparing the differences in these two modeling approaches may be useful for evaluating the relative merits of the two analysis approaches.,

For predictive modeling crossover will not be considered and as “Intent to treat” modeling – where the assigned treatment (in the RCT) or the selected treatment (in the OS) cohorts will be retained throughout the analysis.

Additional baseline covariates may be added to this model depending on the results of preliminary comparison of baseline differences between treatment groups and recursive partitioning methods will explore additional possible baseline factors and interactions among these factors to detect patient profiles that vary across treatment assignment. In addition, significant relationships between baseline variables and crossover status and loss to follow-up will also be useful for identifying covariates.

For the OBS group, where baseline differences between the two treatment groups are expected, the same basic model will be used and the same approach for adding covariates to the model based baseline differences between treatment groups, crossover status and loss to follow-up will be used.

The primary hypothesis of interest concerns differences between treatment outcomes at each time interval and differential change in outcomes within treatment across time intervals. Thus, preplanned follow-up simple effects tests associated with the treatment x interval interaction will be explored even if the interaction itself is not statistically significant (this is what preplanned means).

These simple effects tests will evaluate:

1. Differences in effect size (e.g. d_pcs) at each interval between the two treatment groups (e.g., are the effect sizes between treatment groups at 2 years significantly different?);

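### The observational cohort's stated 80% power for a 0.175 difference uses an unsourced SD of 0.400; on the SAP's own Table 2 SDs of 0.6 to 0.7 it is about 47% to 36%

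*SAP*

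**What the plan says.** **Observational cohort (SAP 1.6.3).** The plan starts from 94 patients preferring each treatment. It moves 10% of the non-operative patients to surgery (85 and 103) and then removes losses: "with 10% lost to follow-up, the final expected cell counts would be 77 and 93". For these counts it specifies "a two-group t-test with a 0.050 two-sided significance level" and states that this "will have 80% power to detect a difference in means of 0.175, assuming that the common standard deviation is 0.400". The sentence names no outcome and gives no origin for 0.400.

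**RCT (SAP 1.6.2).** The SAP says that "Table 2 summarizes estimated sample sizes per treatment needed to achieve power of .80 for 2-tailed testing" at a type I error rate of .05. All six rows use a common SD of 0.6 or 0.7. One of the two scenarios judged most likely is the row "0.4 0.8 0.6 0.667 37" (two means, SD, effect size, patients per group). The other has SD 0.7, effect size 0.714 and 32 per group. The estimates are said to draw on the study group's existing data, "with the mean and standard error estimated adjusted for SRS baseline and patient age gender and Cobb angle".

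**Outcome.** SAP 1.6.2 gives change in SRS-QOL from baseline as the modelled outcome for the observational cohort and says that the RCT will be analysed in the same way.

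**Covariates.** The opening text of SAP 1.6, before 1.6.1, says that the SDs assumed in the sample size calculations took no account of the reduction expected from baseline covariates.

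**Analysis set.** The addendum of 8/29/12 makes intent-to-treat the primary approach for both the RCT and the observational study. In a sentence about predictive modelling it adds that "the selected treatment (in the OS) cohorts will be retained throughout the analysis".

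**The concern.** Two adjacent sections of one SAP plan for what appears to be the same outcome, in patients meeting the same entry criteria, with SDs that differ by a factor of 1.5 to 1.75. The smaller SD has no stated source, and it carries the only power statement for the observational cohort.

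What is at stake is how the cohort's results are read. SAP 1.6.3 intends to use agreement or disagreement between the RCT and the cohort to judge generalizability, and that depends on the cohort's precision. A reader told that power is 80% for 0.175 could give a null cohort result more weight against a difference of that size than the plan's other SDs would allow.

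**Working it through.** **Inputs.** From SAP 1.6.3: n₁ = 77, n₂ = 93, difference δ = 0.175, SD σ = 0.400, two-sided α = 0.05, two-group t-test. From Table 2: σ = 0.6 and 0.7.

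**Formula.** The noncentrality parameter is λ = δ / [σ √(1/n₁ + 1/n₂)]. Power is the probability that a noncentral t variable with n₁ + n₂ − 2 = 168 degrees of freedom falls outside ±1.974.

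Here √(1/77 + 1/93) = 0.1541.

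**Step 1: reproduce the plan's figure.** At σ = 0.400, λ = 0.175 / (0.400 × 0.1541) = 2.84 and power is 80.6% (normal approximation 81.0%). The stated 80% is correct for its inputs.

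**Step 2: check that Table 2 uses the same kind of test.** The smallest equal group size giving 80% power by the same noncentral t calculation is 24, 37, 64, 32, 50 and 87 for the six rows in order. All six match Table 2. The two sections therefore use the same type of calculation and differ in its inputs.

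**Step 3: put the Table 2 SDs into the observational calculation**, with everything else unchanged.

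| SD | λ | Power for 0.175 | Difference detectable at 80% power |
|---|---|---|---|
| 0.4 | 2.84 | 80.6% | 0.174 |
| 0.6 | 1.89 | 46.9% | 0.260 |
| 0.7 | 1.62 | 36.5% | 0.304 |

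By normal approximation with equal groups, 80% power for 0.175 would need about 185 per group at SD 0.6 or 252 at SD 0.7.

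**Step 4: the reverse substitution.** With SD 0.4, the two most likely rows of Table 2 (differences 0.4 and 0.5) would need 17 and 12 per group instead of 37 and 32. The two SDs cannot both stand for the same quantity.

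**Step 5: could covariate adjustment explain 0.400?** If adjustment reduces an SD from σ to σ√(1 − ρ²), reaching 0.400 needs ρ = √(1 − (0.4/σ)²). This is 0.75 from σ = 0.6 and 0.82 from σ = 0.7. The SAP states no such correlation.

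**Step 6: power for the differences in Table 2, with 77 and 93 patients.**

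| Difference | SD 0.6 | SD 0.7 |
|---|---|---|
| 0.3 | 89.7% | 79.0% |
| 0.4 | 99.0% | 95.8% |
| 0.5 | over 99% | 99.6% |

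**Step 7: arm sizes by selected treatment.** Keeping patients in the arm they chose and losing 10% gives 94 × 0.9 = 84.6, about 85 per arm. Power for 0.175 is then 80.9%, 47.2% and 36.7% at SDs 0.4, 0.6 and 0.7, almost the same as in Step 3. It falls to about 72%, 40% and 31% only if one also assumes that 10% crossover shrinks the difference to 0.175 × 0.9 = 0.158. The SAP does not state that assumption.

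**The case against.** **The true SD is unknown.** A reader might infer that the cohort's real power is 36% to 47%. The documents do not support that. The addendum of 1/17/13 itself says that advance variance estimates may be inaccurate. The figures show power under the Table 2 SDs and nothing more. This stands.

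**It is not an arithmetic error.** A reader might also infer a miscalculation. Step 1 shows there is none; the problem is an unexplained conflict between inputs. This stands too.

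**Table 2 may be deliberately conservative.** The opening of SAP 1.6 says that the assumed SDs ignore covariate shrinkage, so a smaller adjusted SD is possible. SAP 1.6.2, however, describes the Table 2 estimates as adjusted, although its wording refers to the mean and standard error and not expressly to the SD. The two statements need reconciling. They lower the certainty of the point, but neither supplies 0.400.

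**The outcome is inferred.** The power sentence does not name SRS-QOL. The inference is strong: 1.6.2 gives that outcome for this cohort, and 0.175 with SD 0.400 suits the 1 to 5 SRS scale. It does not suit the 0 to 100 scales given for the ODI (Protocol 1.5.1) and the SF-12 domains (SAP 1.6.1).

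**The as-treated counts are defensible.** The Protocol's design overview plans as-treated as well as intent-to-treat analyses, so 77 and 93 fit one planned analysis. They do not match the primary one, but Step 7 shows that this alone hardly changes power.

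**The consequence is small.** The documents do not call 0.175 a target or an important difference. The cohort supplements the RCT, the SAP commits to reporting 95% confidence intervals for the longer-term model-predicted changes, and observational enrollment closed in May 2013. All of this stands and keeps the point minor.

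**Conclusion.** The power statement in SAP 1.6.3 does not hold on the SDs that the same SAP uses in Table 2. On those SDs, power for 0.175 is about 47% or 36% instead of 80%, and the difference detectable at 80% power is about 0.26 or 0.30, which is 1.5 to 1.75 times the stated 0.175.

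This rests on two assumptions: that the statement concerns change in SRS-QOL, and that Table 2 is the relevant guide to the SD. If 0.400 is a justified covariate-adjusted SD, the stated power is right, and Table 2 is what needs explaining.

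A reader might go further and call the cohort underpowered. Step 6 does not support that: power is about 79% to over 99% for differences of 0.3 to 0.5. Only the claimed sensitivity to 0.175 fails. The point is minor.

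**What to change.** In SAP 1.6.3, do one of the following:

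- Restate the calculation with the Table 2 SDs: 80% power for a difference of about 0.26 (SD 0.6) to 0.30 (SD 0.7), or equivalently 47% to 36% power for 0.175.
- Keep 0.400, give its source and the covariates behind it, and explain why Table 2 uses 0.6 and 0.7.

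In either case:

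- Name the outcome and the follow-up time in the power sentence.
- Reconcile the opening of SAP 1.6 with 1.6.2 on whether the Table 2 SDs are covariate-adjusted.
- Say that 77 and 93 are as-treated counts, and give about 85 per arm for the intent-to-treat analysis that the 8/29/12 addendum makes primary.

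The cost is SAP wording only. With enrollment closed, no design change follows. The first option makes a stated figure less favourable.
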